### 1.5.2 Efficacy

The efficacy of lefamulin in humans has been demonstrated in a Phase 2 study of 207 subjects with ABSSSI comparing 2 lefamulin doses (100 mg and 150 mg IV) with vancomycin ( $\geq 1000$  mg) over 5-14 days. This study enrolled subjects with moderate to severe skin infection, excluding any subjects with minor and uncomplicated infection. In total, 90.8% of subjects in the modified ITT population had *S. aureus* infection; 69.1% of subjects had MRSA.

In all populations evaluated, lefamulin 100 mg and 150 mg demonstrated consistently high clinical and microbiological success rates at several time points including the Test of Cure (TOC), and 7 to 14 days after the completion of therapy (modified ITT population: 82.0% and 82.4% for 100 mg and 150 mg q12h treatment arms, respectively; 82.4% for vancomycin). The early clinical responder rate (Day 3) for lefamulin was also high and comparable to that of vancomycin.

There were no significant differences in clinical success rates and microbiological eradication rates when assessed by baseline pathogen, particularly *S. aureus* and MRSA. Furthermore, no development of decreasing susceptibility was observed for lefamulin during the study (Paukner et al., 2012; Prince et al., 2013; Rubino et al., 2015).

### 1.5.3 Safety

No changes in safety laboratory parameters, blood pressure (BP), heart rate (HR), or body temperature in any subject at any session in any study were of clinical concern. After IV administration, pain and erythema at the infusion site were the most frequently reported findings. The oral administration of lefamulin was generally well tolerated; infrequent mild and reversible gastrointestinal findings (nausea, abdominal pain and diarrhea) were reported. There were no systemic AEs of clinical concern and no drug-related SAEs in any study conducted to date. None of the subjects met withdrawal criteria. The stopping criteria were not reached in any of the studies.

In the Phase 2 study in subjects with ABSSSI, lefamulin (100 mg and 150 mg) administered intravenously over 5 to 14 days was safe and well tolerated. The incidence of treatment-emergent adverse events (TEAEs) considered related to study drug was numerically lower for subjects treated with lefamulin (34% and 39% in the 100 and 150 mg groups, respectively) than for subjects treated with vancomycin (53%). The types of TEAEs were consistent with a subject population under treatment for ABSSSI. The most frequently reported treatment-related TEAEs in subjects receiving lefamulin were headache, nausea, and diarrhea. Phlebitis at the infusion site was reported in 4 subjects in the lefamulin 100 mg group and 2 subjects in the 150 mg group. There was no increased incidence of phlebitis with increased dose. The most frequently reported treatment-related TEAEs for the vancomycin group were headache, nausea, pruritus, generalized pruritus, and diarrhea. All other related TEAEs were reported by 3 or fewer subjects in each treatment group.

In the Phase 2 study, study drug was discontinued due to an AE for 6 subjects (8 events). These AEs were hyperhidrosis, vomiting, headache, respiratory failure (an SAE), cellulitis, infusion site pain, and dyspnea in the lefamulin groups; and drug eruption in the vancomycin group. Six of these 8 events were considered related to study drug (hyperhidrosis, vomiting, headache, infusion site pain, and dyspnea in the lefamulin groups and drug eruption in the vancomycin group). Five subjects experienced an SAE; none was considered related to study drug. These SAEs were abscess, respiratory failure, and cellulitis in the lefamulin groups; and accidental overdose (narcotics) and convulsion in the vancomycin group (Prince et al., 2013).

The effect of lefamulin on the cardiac conduction parameters of RR, QT, and QTcF has been closely monitored in all clinical studies. A  $C_{max}$ -dependent, predictable, and reproducible prolongation of the QT/QTcF interval has been observed. A thorough analysis of ECGs in the Phase 2 study demonstrated that lefamulin prolonged cardiac depolarization and repolarization duration, but otherwise had a similar cardiac safety profile to that of vancomycin based on evaluations of 12-lead ECGs. Therefore, it is expected that lefamulin will not produce large effects on cardiac de- and repolarization duration. No drug-related cardiac AE — such as increase in ectopic ventricular activity or other cardiac arrhythmia — or clinically relevant ECG findings was reported during the conduct of the studies. None of the protocol-defined stopping criteria (i.e.,  $QTcF > 500$  ms and  $\Delta QTcF > 60$  ms) was reached in any clinical study.

In summary, the results of the Phase 2 study provide the first proof of concept for the systemic use of a pleuromutilin antibiotic in subjects and support the further clinical evaluation of lefamulin for therapy of serious infections. Pharmacokinetic/pharmacodynamics analyses suggest that lefamulin 150 mg IV q12h is an efficacious dosing regimen for Phase 3 studies. Based on available safety data, lefamulin 150 mg IV q12h produced therapeutic exposures and demonstrated an acceptable benefit/risk profile for the treatment of infected subjects. Oral doses of 600 mg lefamulin produced similar systemic exposures to 150 mg IV with a similar benefit/risk profile and were well tolerated with no signs or symptoms of clinical concern.

This is the first Phase 3 study to be conducted in subjects with a systemically-administered pleuromutilin antibiotic. The population in this study will be subjects with CABP and they

will receive treatment with either lefamulin or moxifloxacin (with or without adjunctive linezolid), a standard treatment for this condition.

## 2 STUDY OBJECTIVES

### 2.1 Primary Objectives

- Demonstrate the non-inferiority (NI) of lefamulin versus comparator with respect to the Early Clinical Response ( $96 \pm 24$  hours after the first dose of study drug) in the Intent-to-Treat (ITT) Analysis Set (**FDA endpoint**).
- Demonstrate the NI of lefamulin versus comparator with respect to the Investigator's Assessment of Clinical Response at Test of Cure (TOC) (i.e., 5-10 days after the last dose of study drug) in the modified-ITT (mITT) and Clinically Evaluable at TOC (CE-TOC) Analysis Sets (**EMA endpoint**).

### 2.2 Secondary Objectives

- Evaluate the Early Clinical Response in the Microbiological Intent-to-Treat (microITT) Analysis Set.
- Evaluate the Early Clinical Response PLUS improvement in vital signs in the ITT Analysis Set.
- Evaluate the Investigator's Assessment of Clinical Response at TOC in the microITT and Microbiologically Evaluable at TOC (ME-TOC) Analysis Sets.
- Evaluate the By-Pathogen Microbiologic Response at TOC in the microITT and ME-TOC Analysis Sets.
- Evaluate the safety and tolerability of lefamulin versus comparator in the Safety Analysis Set.
- Evaluate 28 day all-cause mortality in the ITT Analysis Set.

### 2.3 Additional Objectives

- Evaluate the Early Clinical Response by baseline pathogen in the microITT Analysis Set.
- Evaluate the Investigator's Assessment of Clinical Response at the End of Treatment (EOT) (i.e., within 2 days after the last dose of study drug) and at LFU in the mITT and CE-EOT Analysis Sets (CE-EOT for IACR at EOT and CE-LFU for IACR at LFU).
- Evaluate the Investigator's Assessment of Clinical Response by baseline pathogen at TOC and LFU in the microITT and ME-TOC Analysis Sets (ME-TOC for IACR at TOC and ME-LFU for IACR at LFU).
- Evaluate the By-Subject Microbiologic Response at TOC in the microITT and ME-TOC Analysis Sets.
- Evaluate the plasma pharmacokinetics (PK) of lefamulin in the PK Analysis Set.

- Explore a variety of health utilization variables and an investigational patient reported outcome (PRO) measure (SF-12) in subjects receiving lefamulin compared with subjects receiving comparator.

### 3 STUDY DESIGN

This multicenter, multinational, randomized, double-blind, double-dummy, active-controlled efficacy and safety study in subjects with community-acquired bacterial pneumonia (CABP) will be conducted at approximately 125 centers. The planned enrollment is 550 subjects with Pneumonia Outcomes Research Team (PORT) Risk Class  $\geq$ III. However, if based upon regulatory requirements additional subjects exposed to lefamulin are needed, up to 626 subjects may be enrolled. Eligible subjects will be randomized 1:1 to lefamulin or the comparator, moxifloxacin, using interactive response technology (IRT). Subject randomization will be stratified according to PORT Risk Class (Risk Class III vs. IV and V), geographic region (US vs. ex-US), and prior (single dose) short-acting antibiotic therapy for CABP vs. none.

Subjects will be consented for the study prior to study assessments being performed and confirmation of eligibility. Screening assessments will be performed within 24 hours before the first dose of study drug.

Subjects will be assessed for response at the following time points during the study:

- Early Clinical Assessment (ECA):  $96 \pm 24$  hours after the first dose of study drug (i.e., after at least 6 doses of study drug have been given)
- End of Treatment (EOT): within 2 days after the last dose of study drug (NOTE: every attempt should be made to conduct the EOT visit within 1 day after the last dose of study drug. However, if this is not logistically feasible [e.g., visit would need to be conducted over a weekend], then conducting the visit within 2 days is acceptable.)
- Test of Cure (TOC): 5-10 days after the last dose of study drug
- Late Follow Up (LFU):  $30 \pm 3$  days after the first dose of study drug

Assessment of the 4 cardinal symptoms of CABP (dyspnea, cough, purulent sputum production and chest pain) will be conducted daily (see Section 6.10); an assessment at  $96 \pm 24$  hours after the first dose of study drug will be used to determine Early Clinical Response (ECR) (as defined in the Primary Objective - FDA) (Section 9.4.1). NOTE: ECR will be determined programmatically based upon the Investigator's assessment of the 4 cardinal symptoms of CABP; the decision to maintain the subject on study drug therapy will be made by the Investigator, based on all available data and his or her best clinical judgment. CABP signs and symptoms will be assessed in person while subjects are hospitalized. Outpatients may have signs and symptoms assessed daily by telephone; however, they must also have a study site visit  $96 \pm 24$  hours after the first dose of study drug to assess CABP signs and symptoms in person.

In addition, the Investigator's Assessment of Clinical Response (IACR) will be performed at the EOT, TOC, and LFU visits (Success, Failure and Indeterminate at EOT and TOC; Sustained Success, Relapse and Indeterminate at LFU).

Microbiological assessments will be performed at Screening, and throughout the study as clinically indicated (see Section 6.14). Samples will be taken for Gram's staining, for diagnostic tests (serology, urine antigen tests, and molecular tests) and for culture and antimicrobial susceptibility testing.

Safety will be assessed by monitoring vital signs, ECG measurements, safety laboratory parameters, and recording of adverse events (AEs) (see Sections 6.1, 6.4, 6.12, and 7). Safety procedures will be performed by the Investigator or suitably qualified individuals designated by the Investigator. A Data Monitoring Committee (DMC) will review the safety data throughout the study (Section 10.2).

Blood samples for PK analyses will be collected from every subject during administration of IV study drug, and in a subset of subjects who are switched from IV to oral study drug (Section 6.13).

Exploratory evaluation of a variety of health utilization variables (e.g., length of hospital stay, duration of antibiotic therapy, discharge status, discharge destination) as well as a PRO instrument (SF-12) will be performed (Section 6.15).

Overviews of study designs for subjects receiving 7 days of treatment and for subjects receiving 10 days of treatment are presented in Figure 1 and Figure 2, respectively. The schedule of assessments/procedures is presented in Table 3.

### 3.1 Study Rationale

Lefamulin (BC-3781), a semi-synthetic pleuromutilin, represents a new class of antibiotics for the treatment of bacterial infections in humans. Based on the antibacterial spectrum, safety and tolerability and PK in several Phase 1 and Phase 2 clinical studies, lefamulin should be a viable option for the treatment of CABP and other infections. The adverse event profile observed in Phase 1 and 2 studies conducted to date demonstrates that lefamulin is well tolerated when administered IV at single doses up to 400 mg and q12h dosing for up to 10 days. Also, the oral safety profile observed in studies conducted to date demonstrates that 600 mg of lefamulin is well tolerated when administered as single and repeat doses. In the first study in which a systemically available pleuromutilin antibiotic was administered to a patient population, Study NAB-BC-3781-2001, lefamulin was found to be safe and effective in treating skin and skin structure infections and supported the continued clinical evaluation of lefamulin for serious infections. Lefamulin is therefore being examined further in subjects with other infections including CABP.

This study will examine whether lefamulin is non-inferior to moxifloxacin (with or without adjunctive linezolid), for the treatment of CABP in adults  $\geq 18$  years of age. All subjects will initially receive a minimum of 6 doses of IV study medication, after which they may be switched to oral study medication if they meet pre-specified clinical criteria (Section 5.5.3).

The comparison between lefamulin and comparator will be made with respect to the following assessments: ECR ( $96 \pm 24$ h after the first dose of study drug), as well as IACR at TOC. The study will also compare safety between treatment groups and evaluate PK parameters of lefamulin in this population.

This protocol is designed to address both the FDA and European Medicines Agency (EMA) regulatory requirements for the development of antibacterial agents to treat CABP, which differ regarding the preferred primary endpoint. The EMA supports assessment of clinical response by Investigators at a test of cure (TOC) visit, while the FDA adopted assessment of clinical signs and symptoms of CABP on Days 3 to 5 as the recommended primary endpoint. To adequately accommodate these differences, 2 separate regional Statistical Analysis Plans (SAPs) will be utilized to analyze the data collected during this study.

## 4 STUDY POPULATION

### 4.1 Inclusion Criteria

Each subject must:

1. Be male or female  $\geq 18$  years of age.
2. Provide written informed consent and be willing and able to adhere to the study-specified procedures and restrictions. NOTE: Consent may be provided by the subject's legally authorized representative in accordance with local regulations.
3. Have an acute illness ( $\leq 7$  days duration) with at least 3 of the following symptoms consistent with a lower respiratory tract infection (new or worsening):
  - Dyspnea.
  - New or increased cough.
  - Purulent sputum production.
  - Chest pain due to pneumonia.
4. Have at least 2 of the following vital sign abnormalities:
  - Fever (body temperature  $>38.0^{\circ}\text{C}$  ( $100.4^{\circ}\text{F}$ ) measured orally or equivalent temperature from an alternate body site) or hypothermia (body temperature  $<35.0^{\circ}\text{C}$  ( $95.0^{\circ}\text{F}$ ) measured orally or equivalent temperature from an alternate body site).
  - Hypotension (systolic blood pressure  $<90$  mmHg).
  - Tachycardia (heart rate  $>100$  beats/min).
  - Tachypnea (respiratory rate  $>20$  breaths/min).
5. Have at least 1 other clinical sign or laboratory finding of CABP:
  - Hypoxemia (i.e.,  $\text{O}_2$  saturation  $<90\%$  on room air or while receiving supplemental oxygen at subject's baseline requirement or  $\text{PaO}_2 <60$  mmHg).

- Auscultatory and/or percussion findings consistent with pneumonia (e.g., crackles, egophony, dullness).
  - White blood cell (WBC) count  $>10,000$  cells/mm^3 or  $<4500$  cells/mm^3 or  $>15\%$  immature neutrophils (bands) regardless of total WBC count.
6. Have radiographically-documented pneumonia within 48 hours before enrollment (i.e., infiltrates in a lobar or multilobar distribution or diffuse opacities on chest x-ray or chest computed tomography scan consistent with acute bacterial pneumonia).
  7. Have a Pneumonia Outcomes Research Team (PORT) Risk Class  $\geq$ III and require IV antibiotic therapy as initial treatment for the current episode of CABP.
  8. If female, meets the following criteria:
    - Surgically sterile or  $\geq 2$  years postmenopausal, or if of childbearing potential (including being  $< 2$  years postmenopausal), has a negative pregnancy test, and if participating in sexual activity that may lead to pregnancy, agrees to use an effective dual method of contraception (e.g., condom plus diaphragm, condom plus spermicide, intrauterine device plus spermicide) during the study and for  $\geq 28$  days after the last dose of study drug. If a male partner has been surgically sterile for  $\geq 1$  year, a single contraception method may be used. NOTE: The use of contraceptives containing progesterone is not permitted.
    - Agrees not to breastfeed during the study and through  $\geq 28$  days after the last dose of study drug.
  9. If male, meets the following criteria:
    - If not surgically sterile and if participating in sexual activity that may lead to pregnancy, agrees to use an effective dual method of contraception (e.g., condom plus diaphragm, condom plus spermicide, intrauterine device plus spermicide, oral contraceptive plus condom) during the study and through  $\geq 28$  days after the last dose of study drug. If surgically sterile for  $\geq 1$  year, a single contraception method may be used.

## 4.2 Exclusion Criteria

Each subject must NOT:

1. Have received more than a single dose of a short-acting oral or IV antibacterial for CABP within 72 hours before randomization (See Appendix 2).
  - EXCEPTION: Subjects who have received  $>48$  hours of prior systemic antibacterial therapy for the current episode of CABP with unequivocal clinical evidence of treatment failure (i.e., worsening signs and symptoms) and isolation of an organism from blood or respiratory tract that is resistant to the prior systemic antibacterial therapy provided the organism is not resistant to fluoroquinolones and, in the case of methicillin-resistant *Staphylococcus aureus* (MRSA), oxazolidinones.
2. Require concomitant systemic antibacterial therapy potentially effective against CABP pathogens (See Section 6.8).

3. Have been hospitalized for 2 or more days within 90 days prior to the onset of symptoms or have resided in a nursing home or long-term healthcare facility within 30 days prior to the onset of symptoms. NOTE: Residence in an independent living facility is permitted.
4. Have confirmed or suspected CABP caused by a pathogen known to be resistant to any of the study drugs (e.g., *Pseudomonas aeruginosa*, any pathogen of the *Enterobacteriaceae* Family) or attributable to etiologies other than community-acquired bacterial pathogens (e.g., ventilator-associated pneumonia, hospital-acquired bacterial pneumonia, bacterial aspiration pneumonia, *Pneumocystis jiroveci* pneumonia or other fungal pneumonia, viral or mycobacterial infection of the lung).
5. Have a noninfectious cause of pulmonary infiltrates (e.g., pulmonary embolism, chemical pneumonitis from aspiration, hypersensitivity pneumonia, congestive heart failure, bronchial obstruction, lung cancer, cystic fibrosis).
6. Have confirmed or suspected pleural empyema (does not include sterile parapneumonic effusions).
7. Require mechanical ventilation.
8. Have or be at risk for major cardiac events or dysfunction including, but not limited to, the following:
  - Known prolonged QT interval or family history of long QT syndrome
  - Clinically significant hypokalemia which has not been treated prior to randomization
  - Clinically unstable cardiac disease, including: unstable atrial fibrillation, symptomatic bradycardia, unstable congestive heart failure, active myocardial ischemia, or indwelling pacemaker
  - Complete left bundle branch block
  - Receipt within 7 days before enrollment of Class IA or Class III anti-arrhythmic medication or, in the opinion of the Investigator, subject may require such medication during the study. (Class 1A: Quinidine, Procainamide, Disopyramide; Class III: Amiodarone, Dofetilide, Ibutilide, Sotalol)
  - Receipt within 7 days before enrollment of medication that has the potential of prolonging the QT interval or, in the opinion of the Investigator, subject may require such medication during the study (see Appendix 5).
9. Be receiving a strong p-glycoprotein inhibitor or a strong CYP3A inducer or inhibitor (see Appendix 4)
10. Have a history of tendon disease/disorder, myasthenia gravis, or known or suspected central nervous system (CNS) disorders (severe cerebrovascular arteriosclerosis, epilepsy, or other risk factors that may predispose to seizures).
11. Have a history of any hypersensitivity or allergic reaction to any fluoroquinolone or any drug in the pleuromutilin class (i.e., retapamulin).
12. Have severely impaired renal function, defined as creatinine clearance (CrCl)  $\leq 30$  mL/min as calculated by the Cockcroft-Gault formula.

13. Have evidence of significant hepatic, hematologic, or immunologic disease including any of the following:
  - Known acute hepatitis, including active viral hepatitis.
  - Aspartate aminotransferase (AST) or alanine aminotransferase (ALT) level >5 times the upper limit of normal (ULN) or total bilirubin >3 times the ULN.
  - Aspartate aminotransferase (AST) or alanine aminotransferase (ALT) level >3 times the upper limit of normal (ULN) and total bilirubin >2 times the ULN.
  - History of cirrhosis of the liver.
  - Manifestation of end-stage liver disease, such as ascites or hepatic encephalopathy.
  - Current or anticipated neutropenia (<500 neutrophils/mm^3).
  - Thrombocytopenia (<50,000 platelets/mm^3).
  - Known infection with human immunodeficiency virus and a CD4 count <200/mm^3.
14. Have known or suspected severe immunosuppression, defined as receipt of corticosteroid therapy ( $\geq 20$  mg prednisone/day or equivalent for more than 4 weeks) within the previous 8 weeks; solid organ or bone marrow transplantation within the previous 12 months; or currently receiving cytotoxic chemotherapy.
15. Have a life expectancy of  $\leq 3$  months because of any disease other than the current episode of CABP (e.g., current or impending respiratory failure, acute heart failure, shock, acute coronary syndrome, unstable arrhythmia, hypertensive emergency, clinically relevant gastrointestinal bleeding, profound metabolic abnormality, or acute cerebrovascular event).
16. Have participated in any study involving administration of an investigational agent or device within 30 days or  $\leq 5$  terminal elimination half-lives of the previous investigational medicinal product, whichever is longer, before enrollment.
17. Have been previously treated with lefamulin or previously enrolled in this study.
18. Have any condition that, in the opinion of the Investigator, would compromise the safety of the subject or the quality of the data.

**In addition, for subjects suspected to have MRSA for whom adjunctive linezolid or matching placebo will be added, each subject must NOT:**

19. Have received any of the following medications:
  - Monoamine oxidase inhibitors (within 2 weeks of randomization).
  - Serotonergic agents (e.g., SSRI antidepressant medications) (within 5 weeks of randomization).
20. Have pheochromocytoma, carcinoid syndrome, uncontrolled hypertension, or thyrotoxicosis.
21. Have a history of any hypersensitivity or allergic reaction to linezolid or tedizolid.

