## 5.4 Randomization

Qualified subjects will be randomized to receive lefamulin or moxifloxacin in a 1:1 allocation ratio. Randomization may occur at either Screening or on Day 1 prior to receipt of the first dose of study drug. Subjects randomized to IV lefamulin will receive 150 mg of lefamulin q12h and subjects randomized to IV moxifloxacin will receive 400 mg of moxifloxacin q24h. In order to maintain the blind, subjects randomized to IV moxifloxacin will receive alternating doses of IV placebo administered q24h so that IV study drug is administered q12h.

Randomization will be stratified by PORT Risk Class (Risk Class III vs. IV and V; see Section 6.2), geographic region (US vs. ex-US), and prior (single dose) short-acting antibiotic therapy for CABP vs. none using blocked randomization via IRT. (NOTE: No more than 25% of randomized subjects will have received a single dose of a short-acting antibiotic). A minimum of 25% of the total number of subjects randomized will have a PORT risk class of IV or V.

The randomization schedule will be generated by Nabriva (or designee). Subjects randomized into the study will be assigned the treatment corresponding to the next available number in the respective stratum of the computer-generated randomization schedule. Prior to dosing, study personnel will contact the IRT system to obtain a treatment assignment. Subjects are considered randomized once a randomization number has been assigned regardless of whether the subject receives study drug. Randomized subjects who do not receive study drug or who discontinue participation in the study for any reason will not be replaced.

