## 6.8 Prohibited Medications

The following medications are prohibited:

- Prior (within 72 hours before randomization) oral or IV antibacterials for CABP.
  - NOTE: Up to 25% of subjects may have a single dose of a short acting antibiotic for the current episode of CABP within 24 hours of randomization.
  - EXCEPTION: A subject who has received >48 hours of prior systemic antibacterial therapy for the current episode of CABP with unequivocal evidence of treatment failure (i.e., worsening signs and symptoms) and the isolation of an organism from blood or respiratory tract that is resistant to the prior systemic antibacterial therapy, providing the organism is not resistant to fluoroquinolones and, in the case of MRSA, oxazolidinones.
- Agents that prolong the QT interval (see Appendix 5)

- Other systemic antibacterial agents that are potentially effective against pathogens associated with CABP except in the case of treatment failure or when medically necessary for treatment of a concomitant infection.

**NOTE:** The following antibacterial agents are permitted:

- Anti-tuberculosis drugs (exception: Rifampin)
  - Cinoxacin
  - Dapsone
  - Enoxacin
  - Fidaxomicin
  - Methenamine Mandelate
  - Metronidazole
  - Naladixic Acid
  - Nitrofurantoin
  - Norfloxacin
  - Oral Vancomycin
- Systemic corticosteroids at a dose  $\geq 20$  mg per day (prednisone equivalent)
  - Anti-epilepsy or seizure medication
  - Strong p-glycoprotein inhibitors and strong CYP3A inhibitors or inducers (see Appendix 4). [NOTE: The use of contraceptives containing progesterone is not permitted.]
  - Monoamine oxidase inhibitors, serotonergic agents or adrenergic agents (dobutamine, dopamine, epinephrine, norepinephrine, phenylpropanolamine, pseudoephedrine) (only for subjects in whom linezolid is added for MRSA).

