### 9.3.5 Clinically Evaluable Analysis Set

The CE Analysis Sets (CE-EOT, CE-TOC, and CE-LFU Analysis Sets) will be a subset of the ITT Analysis Set that will include subjects who meet the criteria for CABP described in Inclusion Criteria Nos. 3 - 7, and who received at least the pre-specified minimal amount of the intended dose of study drug and duration of treatment, do not have an indeterminate response based on the IACR (at EOT for the CE-EOT Analysis Set, at TOC for the CE-TOC Analysis Set, and at LFU for the CE-LFU Analysis Set), did not receive concomitant antibacterial therapy (other than adjunctive linezolid) that is potentially effective against CABP pathogens (except in the case of clinical failure) from the first dose of study drug through the EOT Visit (CE-EOT Analysis Set), through the TOC Visit (CE-TOC Analysis Set), and through the LFU Visit (CE-LFU Analysis Set), and for whom there are no other confounding factors that interfere with the assessment of the outcome.

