## Appendix 2 Short Acting versus Long Acting Antibiotics

Short-acting	Long-acting
Cephalosporins	
Cefaclor, Cefadroxil, Cefdinir, Cefepime, Cefixime (200 mg), Cefotaxime, Cefpodoxime, Cefprozil, Ceftazidime, Ceftibuten, Cefditoren, Cefruoxime, Cephalexin, Loracarbef	Cefixime (400 mg), Ceftriaxone
Fluoroquinolones	
Ciprofloxacin, Norfloxacin	Gatifloxacin, Gemifloxacin, Grepafloxacin, Levofloxacin, Moxifloxacin, Sparfloxacin
Macrolides and Ketolides	
Clarithromycin, Erythromycin, Roxithromycin	Azithromycin, Clarithromycin XL (extended release), Dirithromycin, Telithromycin
Penicillins and Carbapenems	
Amoxicillin, Amoxicillin-Clavulanate, Amoxicillin-Sulbactam, Ampicillin, Ampicillin-Sulbactam, Dicloxacillin, Imipenem, Meropenem, Nafcillin, Oxacillin, Penicillin-G, Penicillin-V, Piperacillin, Piperacillin-Tazobactam, Ticarcillin-Clavulanate	Ertapenem, Penicillin-G, Benzathine/Procaine
Tetracyclines	
Doxycycline (100 mg), Minocycline, Tetracycline	Doxycycline (200 mg), Minocycline Extended Release

**Appendix 3 Closely Monitored CYP3A4 Substrates and P-Glycoprotein Substrates (excluding strong CYP3A inducers and inhibitors and excluding strong P-glycoprotein inhibitors)**

Closely Monitored CYP3A4 Substrates		
Alfentanyl	Efavirenz	Pimozide
Alprazolam	Eplerenone	Progesterone
Amiodipine	Estradiol	Propranolol
Aprepitant	Fentanyl	Quetiapine
Aripiprazole	Finasteride	Quinine
Astemizole	Gleevec	Reserpine
Buspirone	Haloperidol	Salmeterol
Cafegot	Hydrocortisone	Sildenafil
Caffeine	Lercanidipine	Sirolimus
Chlorpheniramine	Lidocaine	Terfenadine
Cilostazol	Methadone	Testosterone
Cocaine	Midazolam	Trazodone
Codeine	Nateglinide	Triazolam
Dapsone	Nevirapine	Zaleplon
Dexamethasone	Nifedipine	Ziprasidone
Dextromethorphan	Nisoldipine	Zolpidem
Docetaxel	Nitrendipine	
Domperidone	Ondansetron	

Closely Monitored P-Glycoprotein Substrates		
Apixaban	Fexofenadine	Ranitidine
Carvedilol	Fosamprenavir	Rivaroxaban
Cimetidine	Ivermectin	Saxagliptin
Colchicine	Ledipasvir	Silodosin
Dabigatran	Loperamide	Sitagliptin
Daclatasvir	Losartan	Sofosbuvir
Dasabuvir	Maraviroc	Tetracycline
Dexamethasone	Methylprednisolone	Tipranavir
Digoxin	Methotrexate	Tolvaptan
Domperidone	Morphine	Umeclidinium
Edoxaban	Ombitasvir	Vecuronium
Empagliflozin	Paliperidone	Vilanterol
Estradiol	Paritaprevir	
Ezetimibe	Prazosin	

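### Exclusion Criterion 1 and Section 6.8 contradict each other on antibacterials given for CABP before randomization; Exclusion 1 leaves out long-acting agents and uses a different window for the single short-acting dose

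*Protocol*

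**What the plan says.** Exclusion Criterion 1 (Protocol 4.2 and the synopsis) states that a subject must not "Have received more than a single dose of a short-acting oral or IV antibacterial for CABP within 72 hours before randomization", and refers to Appendix 2. An exception follows for documented failure of more than 48 hours of earlier systemic therapy, under conditions on resistance.

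Section 6.8 lists as prohibited "Prior (within 72 hours before randomization) oral or IV antibacterials for CABP", with no limit by duration of action. It allows up to 25% of subjects to have had "a single dose of a short acting antibiotic for the current episode of CABP within 24 hours of randomization" and repeats the treatment-failure exception.

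Appendix 2 sorts antibacterials into short- and long-acting. The long-acting column includes "Cefixime (400 mg), Ceftriaxone" among the cephalosporins and "Gatifloxacin, Gemifloxacin, Grepafloxacin, Levofloxacin, Moxifloxacin, Sparfloxacin" among the fluoroquinolones.

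Section 5.4 stratifies on "prior (single dose) short-acting antibiotic therapy for CABP vs. none using blocked randomization via IRT". It caps at 25% the share of randomized subjects with a single short-acting dose.

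The opening of Section 6 allows enrolment of subjects who meet the Section 4 criteria. Section 9.3.1 keeps every randomized subject in the ITT set. Section 9.3.5 builds the CE sets from "subjects who meet the criteria for CABP described in Inclusion Criteria Nos. 3 - 7", checks concomitant antibacterials from the first study dose onward, and adds a general clause on confounding factors.

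**The concern.** Exclusion 1 points to a two-column appendix but uses only one column. For a long-acting agent it says nothing, while Section 6.8 prohibits it. The two also differ on the permitted short-acting dose: Exclusion 1 sets no limit tighter than 72 hours, and Section 6.8 sets 24 hours.

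Which text a site follows decides who is randomized. Enrolment is tied to Section 4, and Exclusion 1 does not cite Section 6.8. Exclusion 2 does cite it, but for concomitant therapy that the subject will need.

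In a non-inferiority trial this matters in one direction. A subject who already has effective cover tends to respond in either arm, which pulls the treatment difference toward zero. Once randomized, such a subject cannot be taken out of the FDA primary analysis.

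**Working it through.** **1. The two rules side by side** (treatment-failure exception set aside)

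| Therapy for CABP before randomization | Exclusion 1, read literally | Section 6.8 |
|---|---|---|
| None | passes | allowed |
| One short-acting dose within 24 h | passes | allowed |
| One short-acting dose, 24 to 72 h before | passes | prohibited |
| More than one short-acting dose within 72 h | excluded | prohibited |
| Any long-acting dose within 72 h | not mentioned, so passes | prohibited |

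The rules conflict in the third and fifth rows.

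**2. Do other criteria close the gap for long-acting agents?** Only in part. Exclusion 8 bars QT-prolonging drugs within 7 days. Appendix 5 names sparfloxacin and clarithromycin, which reaches two entries of the long-acting column (sparfloxacin and extended-release clarithromycin). The Appendix 5 list is stated not to be exhaustive, but it does not name ceftriaxone, levofloxacin or moxifloxacin. Exclusion 18 is left to the investigator's judgement.

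**3. What happens to such a subject after randomization?** The stratum has two levels, "prior (single dose) short-acting antibiotic therapy for CABP vs. none", and neither describes a long-acting dose. If the subject is entered as having had none, Section 9.6 keeps that stratum in the stratified analyses. The 25% cap counts only short-acting single doses. ITT retains the subject.

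**4. Reproducing the plan's power.** Inputs from Section 9.2, Table 11 and Section 9.6.1: 275 per arm, one-sided alpha 0.025, continuity-corrected Z; ECR 79% with margin 12.5%; IACR 80% (mITT) and 85% (CE-TOC, 220 per arm) with margin 10%. With equal true rates p, SE = √(2p(1−p)/n), correction c = 1/n, and power = Φ((margin − c)/SE − 1.96).

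- ECR: SE = √(2 × 0.79 × 0.21/275) = 0.0347; (0.125 − 0.0036)/0.0347 − 1.96 = 1.53; power 93.75% (stated 93.8%).
- IACR mITT: 80.65% (stated 80.6%).
- IACR CE-TOC: 80.06% (stated 80%).

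The stated power is reproduced and is not in question.

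**5. How much could pre-treated subjects matter?** The protocol gives no share f, so this is a hypothetical. Assume that lefamulin is worse by the full 12.5 points in subjects without prior cover, that the arms do not differ in the pre-treated share f, and that the control rate is 79%. The overall deficit is then 12.5 × (1 − f) points and the lefamulin rate is p₁ = 0.79 − 0.125(1 − f). With SE = √((0.79 × 0.21 + p₁(1 − p₁))/275),

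P(declare NI) = Φ((0.125f − 1/275)/SE − 1.96).

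| f | Overall deficit (points) | P(declare NI), ECR |
|---|---|---|
| 0 | 12.5 | 2.0% |
| 1% | 12.4 | 2.2% |
| 5% | 11.9 | 2.9% |
| 10% | 11.25 | 4.3% |

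Example for f = 10%: p₁ = 0.6775, SE = 0.0374, (0.0125 − 0.0036)/0.0374 − 1.96 = −1.72, which gives 4.3%. The value at f = 0 is below 2.5% because of the continuity correction.

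**The case against.** The strongest reply is that the protocol, read as a whole, does not admit these subjects. Section 6.8 prohibits them outright. The exception in Exclusion 1 covers prior systemic therapy of any class, and for long-acting agents it would be needless if they were already allowed. The stratum and the cap both treat one short-acting dose as the most that is permitted, so the missing stratum level is better read as a sign of intent than as a second defect. All of this stands. A reader might infer from Exclusion 1 that subjects pre-treated with ceftriaxone or moxifloxacin are eligible by design; the documents do not support that.

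Three other strong readings also fail.

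- The gap does not cover the whole long-acting class, because Exclusion 8 removes some agents.
- It does not follow that the CE sets lack protection. The clause on confounding factors is there, its details are commonly left to the SAP, and the SAP is not at hand. Inclusion 7, which requires a need for IV therapy as initial treatment, is also checked for these sets and might not be met after several earlier doses.
- Setting f at 25% gives 11.2% in the same calculation, but 25% is the cap on a different, permitted group. With Section 6.8 in force, f should be small.

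The reply does not remove the contradiction itself. Intent has to be pieced together from other sections, while the criterion that a site checks at enrolment says less than the design needs.

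**Conclusion.** The concern holds as an internal contradiction in the eligibility rules, of moderate weight. Exclusion 1 (in 4.2 and the synopsis) and Section 6.8 differ on agent class and on the window for the single short-acting dose. Because enrolment is tied to Section 4, sites can apply the rules differently, and a subject wrongly randomized stays in the ITT primary analysis without a proper stratum and outside the cap.

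The direction of any bias is toward non-inferiority. Its size is not known. Under the assumptions shown, it is negligible at f = 1% (2.2% against 2.0%) and roughly doubles the chance of a false ECR conclusion at f = 10% (4.3%). These figures illustrate sensitivity and do not predict what will happen. They concern ECR only; the EMA conclusion uses a stratified Miettinen-Nurminen interval and needs success in both mITT and CE-TOC.

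**What to change.** Reconcile Exclusion 1 in Section 4.2, its copy in the synopsis and Section 6.8 into one eligibility statement. It should settle three things explicitly: which agent classes it covers (both columns of Appendix 2), how many doses, and the look-back window, including the difference between 72 and 24 hours for the single short-acting dose. Which rule applies is for the sponsor to decide; the point is that all three places must say the same.

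Then align the IRT eligibility and stratification check with that statement, so that every subject who can be randomized belongs to a defined level of the prior-antibiotic factor and is counted correctly against the cap.

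The cost is amendment wording and one IRT question. Sample size, power, margins and analysis methods stay as they are. Because the ITT set cannot be corrected afterwards, the change should be in place before subjects are randomized under the present wording.
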